## 1 List of Abbreviations

ABC-2	Aberrant Behavior Checklist-2
AE	Adverse Event
AMSE	Autism Mental Status Exam
APTT	Activated Partial Thromboplastin Time
ASD	Autism Spectrum Disorder
ATC	Anatomical/Therapeutic/Chemical
AUC	Area under the plasma concentration-time curve
BID	Twice-a-day
BPI-SF	Behavior Problems Inventory - Short Form
CFR	Code of Federal Regulations
CGI-I	Clinical Global Impression - Improvement
CGI-S	Clinical Global Impression - Severity
CRF	Case Report Form
CRO	Contract Research Organization
CSHQ	Child Sleep Habits Questionnaire
CSR	Clinical Study Report
COVID-19	Coronavirus-19
DSM5	Diagnostic and Statistical Manual of Mental Disorders
DSMC	Data Safety Monitoring Committee
ECG	Electrocardiogram
EDC	Electronic Data Capture
EGFR	Estimated Glomerular Filtration Rate
EOT	End of Treatment
ET	Early Termination
FDA	Food and Drug Administration
GCP	Good Clinical Practice
GIHQ	Gastrointestinal Health Questionnaire
GLP	Good Laboratory Practice

GMP	Good Medical Practice
IB	Investigator's Brochure
ICF	Informed Consent Form
ICH	International Conference on Harmonization
ICND	Impact of Childhood Neurological Disability
IEC	Independent Ethics Committee
IMP	Investigational Medicinal Product
INR	International Normalized Ratio
IRB	Institutional Review Board
ITT	Intent-to-Treat Population
MB-CDI	MacArthur-Bates Communicative Development Inventory
MedDRA	Medical Dictionary of Regulatory Affairs
NVDQ	BSID-4 nonverbal development quotient
NVIQ	SB5 nonverbal z-deviation IQ
PT	Prothrombin Time
QI-Disability	Quality of Life Inventory - Disability
SAE	Serious Adverse Event
SAF	Safety Population
SAP	Statistical Analysis Plan
SB5	Stanford-Binet Intelligence Scales version 5
SD	Standard Deviation
SOC	System Organ Class
SOP	Standard Operating Procedure
ORCA	Observer-Reported Communication Assessment
РК	Pharmacokinetics
PMS	Phelan McDermid Syndrome
PMS-DSRS	PMS Clinician Domain Specific Rating Scale
PP	Per-Protocol Population
TEAE	Treatment-Emergent Adverse Event

TFLs	Tables, Figures, and Listings
TSH	Thyroid-Stimulating Hormone
UR	Urine
WHO	World Health Organization

## 2 Introduction

Neuren Pharmaceuticals Ltd. is conducting a study to investigate a new treatment for Pitt-Hopkins Syndrome (PTHS). The study background, design and subject assessments for the study are described in the study specific protocol.

The statistical methods to be implemented during the analyses of data collected within the scope of this study will be outlined in this document. The purpose of this plan is to provide specific guidelines from which the statistical analysis will proceed. This statistical analysis plan (SAP) is to be interpreted in conjunction with the protocol. Should the SAP and protocol be inconsistent with respect to the planned analyses, the language of the SAP is governing. Any deviations from this plan will be documented in the clinical study report (CSR).

The statistical principles applied in the design and planned analyses of this study are consistent with the International Conference on Harmonisation (ICH) guidelines E9 (Statistical Principles for Clinical Trials).

## 2.1 Study Objectives

The primary objective of this study is to investigate the safety, tolerability, and pharmacokinetics of treatment with NNZ-2591 Oral Solution, 50mg/mL Investigational Medicinal Product (IMP) in children and adolescents with Pitt-Hopkins Syndrome.

The secondary objective of this study is to investigate measures of efficacy during treatment with NNZ-2591 Oral Solution, 50mg/mL IMP in children and adolescents with Pitt-Hopkins Syndrome.

#### 2.2 Study Design

This is a Phase 2, open-label study of the safety and tolerability of NNZ-2591 Oral Solution, 50mg/mL IMP in male and female children and adolescents with Pitt-Hopkins syndrome. Approximately 10-20 male and female subjects between the ages of 3 and 17 years were planned to be enrolled and receive treatment of NNZ-2591 Oral Solution, 50mg/mL IMP for a total of 13 weeks.

There will be a total of 17 study visits, comprising 5 in-clinic visits and 12 remote telemedicine/in-home nurse visits. The study will commence with an approximately 4-6 week Screening and Baseline period. During this Screening/Baseline period, subjects are assessed for study eligibility and data is collected to establish the subject's baseline characteristics and symptom severity using a variety of assessments. Two in-clinic visits and one remote/in-home visit (Visits 1, 2, 3) comprise Screening and Baseline.

Once eligibility is confirmed, subjects are dosed with the starting dose of 4 mg/kg and then be up-titrated to the target dose. Subjects receive IMP for a total of 13 weeks. During the treatment period, there are three in-clinic visits: Week 2 (Visit 5), Week 6 (Visit 9) and Week 13 (Visit 16). There is a combined telemedicine/in-home visit by the site Investigator and an in-home visit by a visiting nurse for safety at Week 1 (Visit 4), Week 4 (Visit 7), Week 8 (Visit 11) and Week 10 (Visit 13). Ideally, these combination telemedicine/in-home visits will be conducted simultaneously whenever possible, or they will be conducted on the same day with the telemedicine visit occurring first. If this is not feasible the in-home and telemedicine components can be conducted over two consecutive days. In-home visits with a visiting nurse will be done at Weeks 3 (Visit 6), 5 (Visit 8), 7 (Visit 10), 9 (Visit 12), 11 (Visit 14), and 12 (Visit 15).

All subjects will also have a combined telemedicine/in-home follow-up visit with the Investigator via telemedicine and an in-person home visit by a visiting nurse approximately 2 weeks after the end of treatment (Week 15, Visit 17).

For all visits designated as in-clinic, an in-person visit is preferred. Off-site assessments may be allowed due to extenuating circumstances due to the COVID-19 health emergency. All requests for off-site assessments must be approved in advance by the Sponsor or Medical Monitor. A combined remote visit or nurse-only in-home visit may be conducted in-clinic by the study staff if agreed upon by the Investigator and the caregiver.

Subjects will be divided into three groups by age for enrollment:

- 13 to 17 years old (Group 1)
- 8 to 12 years old (Group 2)
- 3 to 7 years old (Group 3)

Enrollment commenced with the oldest age group and proceeded as follows. After at least three subjects in Group 1 have received two weeks of treatment at the starting dose, the Data Safety Monitoring Committee (DSMC) will review data on safety and tolerability. If tolerability and safety for those subjects during the specified period is deemed acceptable, enrollment for Group 2 will proceed and dosing will begin at the starting dose. When at least three subjects in Group 2 have received the first two weeks of treatment at the starting dose, the DSMC will review data on safety and tolerability. If tolerability and safety for Group 2 is deemed acceptable, enrollment for Group 3 will commence and dosing will begin at the starting dose.

A summary of the schedule of events and assessments is provided in Table 1 below.

Statistical Analysis Plan 30APR2024

The table of Events and Assessments is from version 2.2 which included ophthalmic exam at week 2 and week 6 (as did version 2.0 and 2.1). This was removed in version 3.0. Since the majority of participants were enrolled on versions 2.0-2.2, and none were enrolled under version 3.0, the 2.2 version has been included in the SAP.

#### Table 1: Schedule of Events and Assessments for Neu-2591-PTHS

Period	Screening	g/ Baseline a	Baseline	Baseline Treatment Period													
	4-6 weeks	i															
Visit Week	-4 to -6	2 weeks from Visit 1	0	1	2	3	4	5	6	7	8	9	10	11	12	13/EOT a	15
Visit Number	1	2	3	4	5	6	7	8	9	10	11	12	13	14	15	16	17
Visit window (days)	±1ª	±1ª	±1ª	±1	±2	±1	±1	±1	±2	±1	±1	±1	±1	±1	±1	-3	+4
Type of Visit	Clinic	Remote and In- Home c,d	Clinic	Remote and In- Home c,d	Clinic	In- Home d	Remote and In- Home c,d	In- home d	Clinic	In- Home d	Remote and In- Home c,d	In- Home d	Remote and In- Home c,d	In- Home d	In- home d	Clinic	Remote and In- Home c,d
Informed consent	X																
Inclusion/exclu sion criteria	X		X														
Medical history	X	Х	Х														
Confirm documented PTHS diagnosis and genotype	X																

Period	Screening	g/ Baseline a	Baseline	Treatment Period													
	4-6 weeks	i															
Visit Week	-4 to -6	2 weeks from Visit 1	0	1	2	3	4	5	6	7	8	9	10	11	12	13/EOT a	15
Visit Number	1	2	3	4	5	6	7	8	9	10	11	12	13	14	15	16	17
Visit window (days)	±1ª	±1ª	±1ª	±1	±2	±1	±1	±1	±2	±1	±1	±1	±1	±1	±1	-3	+4
PTHS history and exam	X																
Confirm co- morbid psychiatric disorders by DSM-5	X																
Rapid SARS- CoV-2 test	X		Х													Х	
Autism Mental Status Exam	X															X	
Recent clinical history				X	X		X		X		X		X			X	X
Physical examination f	X		Х		Х		X g		Х		X g		X g			Х	X g

Period	Screening	/ Baseline a	Baseline	Treatmo	Treatment Period														
	4-6 weeks																		
Visit Week	-4 to -6	2 weeks from Visit 1	0	1	2	3	4	5	6	7	8	9	10	11	12	13/EOT a	15		
Visit Number	1	2	3	4	5	6	7	8	9	10	11	12	13	14	15	16	17		
Visit window (days)	±1ª	±1ª	±1ª	±1	±2	±1	±1	±1	±2	±1	±1	±1	±1	±1	±1	-3	+4		
Neurological examination	X		X		X		X g		X		X g		X g			X	X g		
	X															X			
Abdominal/ CVA/General Appearance f		N		N		N	N	N		N	N	N	N	N	N		N		
Ophthalmic examination h	X				X				X							X			
Vital signs	X	N	Х	N	X	N	N	N	X	N	N	N	N	N	N	X	N		
Height/length	X		X													X			
Weight	X	N	X	N	X	N	N	N	X	N	N	N	N	N	N	X	N		
Review for AEs/SAEs i				X,N	X	N	X,N	N	X	N	X,N	N	X,N	N	N	X	X,N		

Period	Screening/ Baseline a 4-6 weeks		Baseline	Treatm	ent Period												Follow- up b
Visit Week	-4 to -6	2 weeks from Visit 1	0	1	2	3	4	5	6	7	8	9	10	11	12	13/EOT a	15
Visit Number	1	2	3	4	5	6	7	8	9	10	11	12	13	14	15	16	17
Visit window (days)	±1 a	±1ª	±1ª	±1	±2	±1	±1	±1	±2	±1	±1	±1	±1	±1	±1	-3	+4
Caregiver Diary (dosing, conmeds, voids, seizures, changes in symptoms/ tolerability)	X	X	X	X	X	X	X	X	X	X	X	X	X	X	X	X	X
Review Dosing Compliance				X,N	X	N	X,N	N	X	N	X,N	N	X,N	N	N	X	X,N
In-clinic administration of first dose j			X														
12-lead electrocardiogr am (ECG)	X		X		X				X							X	N
CBC with differential	Х		X		X		N		X		N		N			X	N

Period	Screening	g/ Baseline a	Baseline	Treatment Period													Follow- up b
	4-6 weeks																
Visit Week	-4 to -6	2 weeks from Visit 1	0	1	2	3	4	5	6	7	8	9	10	11	12	13/EOT a	15
Visit Number	1	2	3	4	5	6	7	8	9	10	11	12	13	14	15	16	17
Visit window (days)	±1ª	±1ª	±1ª	±1	±2	±1	±1	±1	±2	±1	±1	±1	±1	±1	±1	-3	+4
Coagulation	Х		X		X		N		X		N		N			X	N
Comprehensive Metabolic Panel k	Х		X	N	X	N	N	N	X	N	N	N	N	N	N	X	N
Urinalysis 	Х		X	N	X	N	N	N	X	N	N	N	N	N	N	X	N
Urinalysis- Drugs of Abuse 	X																
TSH, Free T3, Free T4	X															X	
HbA1c	Х															X	
Serum pregnancy test m	Х								Х							X	
Blood samples for					X				X							X	

Period	Screening	/ Baseline a	Baseline	Treatment Period													Follow- up b
	4-6 weeks																
Visit Week	-4 to -6	2 weeks from Visit 1	0	1	2	3	4	5	6	7	8	9	10	11	12	13/EOT a	15
Visit Number	1	2	3	4	5	6	7	8	9	10	11	12	13	14	15	16	17
Visit window (days)	±1ª	±1 a	±1ª	±1	±2	±1	±1	±1	±2	±1	±1	±1	±1	±1	±1	-3	+4
pharmacokineti cs																	
Blood sample for biomarkers	Х		Х													Х	
Stool sample for microbiome	Х		Х													Х	
CGI-I									X							X	X
CGI-S	Х		Х						Х							Х	Х
Stanford-Binet Intelligence Scales version 5 (SB5) or Bayley Scales of Infant Development ver 4 n	X															X	

Period	Screening	g/ Baseline a	Baseline	Treatme	nt Period												Follow- up b
	4-6 weeks																
Visit Week	-4 to -6	2 weeks from Visit 1	0	1	2	3	4	5	6	7	8	9	10	11	12	13/EOT a	15
Visit Number	1	2	3	4	5	6	7	8	9	10	11	12	13	14	15	16	17
Visit window (days)	±1ª	±1ª	±1ª	±1	±2	±1	±1	±1	±2	±1	±1	±1	±1	±1	±1	-3	+4
MB-CDI			Х													X	
ORCA			Х													Х	
Caregiver Top 3 Concerns	Х	Х	Х						Х							Х	X
ABC-2	X	X	Х						X							X	Х
Behavior Problems Inventory-Short Form (BPI-SF)			X													X	
Caregiver Impression of Change																X	
Quality of Life Inventory- Disability (QI- Disability)			X													X	

Period	Screening	g/ Baseline a	Baseline	Treatme	ent Period												Follow- up b
	4-6 weeks																
Visit Week	-4 to -6	2 weeks from Visit 1	0	1	2	3	4	5	6	7	8	9	10	11	12	13/EOT a	15
Visit Number	1	2	3	4	5	6	7	8	9	10	11	12	13	14	15	16	17
Visit window (days)	±1ª	±1ª	±1ª	±1	±2	±1	±1	±1	±2	±1	±1	±1	±1	±1	±1	-3	+4
Impact of Childhood Neurological Disability- Overall quality of life rating			X													X	
CSHQ	X	Х	Х						X							X	X
Vineland Adaptive Behavior Scales-3			X													X	
GIHQ	X	X	Х						Х							X	X
Modified two- minute walk test	X		X													X	
Study Exit Form																	X°

Statistical Analysis Plan 30APR2024

X = Conducted by site personnel or caregiver as applicable

N = Conducted by visiting nurse

Abbreviations: ABC-2, Aberrant Behavior Checklist-2; AE, adverse event; Behavior Problems Inventory-Short Form; BPI-SF; CBC: Complete Blood Count; CGI-I, Clinical Global Impression Scale-Improvement; CGI-S, Clinical Global Impression Scale-Severity; CMP: Comprehensive Metabolic Panel; CSHQ, Child Sleep Habits Questionnaire; DSM-5, Diagnostic and Statistical Manual of Mental Disorders, Fifth Edition; EOT, end of treatment; GIHQ, GI Health Questionnaire; ICND, Impact of Childhood Neurological Disability; IMP, Investigational Medicinal Product; MB-CDI, MacArthur-Bates Communicative Development Inventory; ORCA, Observer-Reported Communication Assessment; PTHS, Pitt-Hopkins syndrome; QI-Disability, Quality of Life Inventory- Disability; SAE, serious adverse events; Stanford Binet Intelligence Scales ver 5

a The Screening/Baseline period will be conducted over 4-6 weeks. The second visit during the Screening period (Visit 2) should be conducted 2 weeks after the Screening visit (Visit 1)  $\pm$  1 day. The subject will then remain in Screening for an additional 2-4 weeks. The caregiver diary must be completed daily during the entire Screening period whether it is 4 weeks or 6 weeks. The Screening visit (Visit 1) and Baseline visit (Visit 3) may be conducted over two days. It is preferable that ECGs, safety labs and biomarker sample collection are conducted on the same day. No assessments can be conducted until after informed consent has been given by the caregiver or legal guardian. Also, training for the caregivers on all caregiver completed assessments must be done before the caregiver rater may complete the assessments. All assessments must be done within the two-day window for the visit (visit day + or - 1 day). For Visit 3, all assessments must be done before administration of the IMP.

b Also for early termination. Subjects who have received IMP for longer than 2 weeks and discontinue prematurely any time after Visit 5 should return to the investigational site for final safety and efficacy assessments as scheduled for the End of Treatment visit (Visit 16) and complete the study exit form.

c This is a combined remote and in-person nurse visit. The remote visit is conducted by the site via telemedicine or video facilities as appropriate. Any caregiver-completed assessments should be completed the same day of the visit or no earlier than the day before the visit (except the Caregiver Diary which is completed daily) and reviewed by the Investigator. A modified version of the physical and neurological exam will be done at the remote visits based on the guidance document provided to the Investigator. At Week 4, the site will inform the caregiver of the dose titration. See Section 9.2.

d In-home visits will be conducted by a visiting nurse. At every nurse visit, the nurse will collect urine, vital signs including weight, and blood samples for a comprehensive metabolic panel (CMP). They will also conduct an exam assessing general appearance, abdominal/costovertebral angle tenderness, and edema. A suprapubic exam for bladder palpation may be done if decreased urine output is reported. The visiting nurse will also review the dosing diary, query oral intake, and do a review of tolerability. Blood samples for CBC with differential and coagulation will be collected at Weeks 4, 8, 10 and Week 15. At the post-treatment follow-up visit at week 15, the visiting nurse will also collect ECG, in addition to the above assessments. At Week 7, the site will also have a phone call with the caregiver to inform him/her of the dose titration. The site will also inform the visiting nurse so the dosing schedule can be reviewed with the family during the in-home visit. See Section 9.1 and Section 9.2.

e A clinic visit is preferred but an off-site visit may be conducted for a scheduled in-clinic visit in extenuating circumstances due to the COVID-19 health crisis. All requests for off-site visit assessments due to extenuating circumstances must be approved in advance by the Sponsor or Medical Monitor.

f The in-clinic physical exam will include an abdominal exam and an assessment of costovertebral angle tenderness (CVA). A suprapubic exam for bladder palpation may be done if decreased urine output is reported. General awareness will be captured as part of the neurological exam. For in-home nursing visits, the nurse will do an exam assessing general appearance (e.g., alertness), an abdominal/CVA, and edema. A suprapubic exam for bladder palpation may be done if decreased urine output is reported.

g A modified version of the neurological and physical exam will be done for the remote visit based on the guidance document provided to the Investigator.

h A complete ophthalmological exam will be conducted by an ophthalmologist at Screening (Visit 1) and End of Treatment (Week 13, Visit 16). Abrief exam (undilated fundoscopy exam) will be done by the ophthalmologist at Week 2 and Week 6. See section 9.5.7).

i The visiting nurse will query any changes in tolerability during the in-home visit. Any changes will be noted and provided to the Investigator. The Investigator will also query changes in tolerability and note any changes in the remote assessment. The Investigator is responsible for determining and reporting any changes that qualify as Adverse Events.

j The first dose of IMP will be administered in the clinic after all Baseline assessments are completed, or, if the Investigator judges that it is too late in the day, on the following day. The subject should be monitored for at least three hours post first dose. Day 1 of dosing is defined by the date when the first dose is taken. At the visit, the site will dispense an adequate supply of IMP for dispensing by the caregiver at home.

k A Comprehensive Metabolic Panel will be assessed every post-enrollment visit (see Section 9.5.2). If abnormal findings are observed on renal or liver function tests, additional tests as is clinically indicated may be conducted as described in Sections 9.5.2.1 and 9.5.2.3).

Drugs of abuse will be evaluated at Screening (See Section 9.5.2).

- m For female subjects who have reached menarche.
- n The Bayley is done for subjects who cannot obtain a basal score on SB5.
- ° The study exit form should also be completed if the subject terminates the study early.

#### 2.2.1 Study Treatment

The total administration period for NNZ-2591 Oral Solution, 50 mg/mL Investigational Medicinal Product (IMP) is 13 weeks. Following up-titration, the IMP is administered open-label at the target dose of 12 mg/kg BID.

The DSMC reviews the clinical safety data prior to any individual dose titration and prior to initiation of subsequent age groups. For dose titration, after a subject has had two weeks of dosing at the dose level, the data is reviewed by the DSMC during which time the subject stays on their current dose. As outlined below in Table 2, the IMP is administered at a starting dose of 4 mg/kg BID for up to 3 weeks. Following DSMC review and approval of each dose titration, subjects are up-titrated to 8 mg/kg BID for up to 3 weeks, and then to the 12 mg/kg BID dose. The subject then continues on the assigned dose (or highest dose tolerated) for the remainder of the 13 weeks.

#### **Table 2: Dose Titration Schedule**

Week 1 and Week 2	Week 3	Week 4 and Week 5	Week 6	Week 7 and Week 8	Week 9	Week 10 to Week 13
4 mg/kg BID (8 mg/kg daily)	4 mg/kg BID (8mg/kg daily) 	8 mg/kg BID (16 mg/kg daily)	8 mg/kg BID (16 mg/kg daily) 	12 mg/kg BID (24 mg/kg daily)	12 mg/kg BID (24 mg/kg daily)	12 mg/kg BID (24 mg/kg daily)
	DSMC Review Data Prior to Up- Titration 		DSMC Review Data Prior to Up- Titration 		DSMC Reviews Data After 2 weeks on 12 mg/kg to Confirm Safety 	

Subjects will stay on their current dose until the data is reviewed by the Data Safety Monitoring Committee (DSMC)

Expected time for DSMC review will be one week.

Subjects who are unable to tolerate the study treatment may be discontinued from the study.

# **3** Analysis Populations

**Intent to Treat Population (ITT)**: The Intent to Treat population will consist of all subjects deemed eligible and enrolled into the study.

**Safety Population (SAF)**: The Safety population will consist of all subjects in the ITT population who received at least one dose of IMP.

**Modified Intent to Treat Population (mITT)**: The modified Intent to Treat population will consist of all subjects in the ITT population who completed treatment and completed the EOT visit.

The pharmacokinetic analyses will be described in a separate analysis plan and summarized separately.

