9.4.5 Early Discontinuation

Investigational Medicinal Product administration may be stopped early if an AE, tolerability issue or inter-current illness occurs that in the opinion of the Investigator (or designee) necessitates cessation of the IMP. Study drug administration must be ceased for all SAEs considered related to the experimental medication.

Note that early cessation of IMP does not necessarily mean the participant is withdrawn from the study. With any early cessation, all evaluations and tests scheduled during the study must be conducted if possible.

- Requests early discontinuation.
- requires treatment with an excluded medication, as defined in Exclusion Criteria (Section 8.2).
- at any point in the study, a participant becomes ill with symptoms of/or tests positive for COVID-19 infection.
- has a positive pregnancy test or becomes pregnant.
- in the Investigator's opinion, the participant is experiencing a clinically significant deterioration in his or her clinical state.
- experiences a Serious Adverse Event deemed to be related to the IMP.
- experiences a severe adverse event deemed to be related to the IMP.
- has an increase in post-enrollment QTcF interval as defined below (see also Section 9.5.8).

Investigational Medicinal Product must be discontinued at any time during the study in the event any of the following are observed post-enrollment:

QTcF Criteria

- A post-enrollment QTcF duration of ≥ 500 ms confirmed by repeat continuous ECG.
- A clinically significant increase of ≥ 60 ms (confirmed by repeat continuous ECG) compared to the average QTcF interval at Baseline (before dosing) is observed.

Participants who have received IMP for longer than 2 weeks and discontinue prematurely any time after Visit 5 should return to the investigational site for final safety and efficacy assessments as scheduled for the EOT visit (Week 13, Visit 16) and complete the study exit form.

Participants who discontinue from the trial prior to receiving any treatment or who discontinue after having received treatment only up to Visit 5 (Week 2 post-baseline) may be replaced.

Participants with early treatment cessation due to SAEs must be followed-up and provided appropriate medical care until their signs and symptoms have remitted or stabilized, or for the remaining study period (until study end), whichever comes sooner. "Study end" is when all participants have completed the study.

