### 5.2.5 Post-Baseline Values

For subjects who discontinue the study, data will be analyzed up to the last observation for safety and efficacy measures. Missing data for safety assessments will not be imputed. For efficacy rating scale measures other than the exceptions listed below, if an assessment has been completed but has missing items, missing values shall be imputed as follows:

- If 3 or fewer items are missing, the last observation for that particular data element (e.g., item response) will be carried forward.
- The scoring algorithms will be applied including the observed values and last observation carried forward (LOCF) for the missing items

These rules will only apply to individual items. Total scores, subdomain and subscale scores will not be carried forward. If the assessment is completely missing, items will not be imputed.

These imputation rules do not apply to the CGI-I, Clinical Global Impression Scale – Severity (CGI-S) or Caregiver Impression of Change assessments. If a particular domain is missing for these assessments, the participant will be excluded from the corresponding analysis. These imputation rules also do not apply to the Caregiver Top 3 Concerns assessment. If a concern is missing for this assessment, the average severity will still be calculated from all non-missing concern severity scores.

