# 8 Efficacy Analysis

The secondary objective is to investigate measures of efficacy during treatment with NNZ-2591 Oral Solution in children and adolescents with PTHS.

All efficacy analyses will be conducted on the ITT and mITT populations.

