A correlation analysis of the efficacy measures will be done using Pearson correlation coefficients at Baseline and EOT. The correlation of each total score will be measured against the others and presented in a table and a heat map/matrix. CGI-I and CGI-S domain scores will also be included in the correlation analysis. Test-retest reliability will be assessed for continuous efficacy assessments collected more than once during the Screening period (Visits 1, 2, and 3, pre-dosing) using Intraclass Correlation Coefficients

Statistical Analysis Plan 30APR2024

(ICC). The ICC will be based on covariance parameter estimates from a Restricted Maximum Likelihood Mixed Model including results from assessments conducted during the Screening/Baseline period with a random effect for subject. The ICC will be derived as: ICC = Within-subject covariance/Total covariance. ICC values range from 0 to 1, with values closer to 1 indicating greater test-retest reliability.

A treatment policy estimand will be used for all endpoints. The variables of interest are numeric scores associated with subject responses. Summaries will be performed on the observed data. There will be no imputations for completely missing scores or intercurrent events. Handling of missing responses items that contribute to total and subscale scores are defined in Section 5.2.5.

Results for each efficacy variable will also be listed by subject.

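### The mITT set is a completers set and cannot estimate the treatment-policy effect that the SAP claims for every endpoint; the parallel ITT analysis can, but it is not named as the main one

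*SAP*

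**What the plan says.** SAP section 3 defines two sets used for efficacy. For the first: "The Intent to Treat population will consist of all subjects deemed eligible and enrolled into the study". The second, called modified ITT, is "all subjects in the ITT population who completed treatment and completed the EOT visit".

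SAP section 8 states: "All efficacy analyses will be conducted on the ITT and mITT populations". Section 9.2 adds that all figures are produced on both. Nothing says which set is main and which is supplementary.

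On the estimand, SAP section 9.2 states: "A treatment policy estimand will be used for all endpoints". It works from observed data: "There will be no imputations for completely missing scores or intercurrent events". SAP section 5.2.5 says: "For subjects who discontinue the study, data will be analyzed up to the last observation for safety and efficacy measures".

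Protocol section 9.4.5 plans to collect data after treatment stops: "With any early cessation, all evaluations and tests scheduled during the study must be conducted if possible". It also says: "Participants who have received IMP for longer than 2 weeks and discontinue prematurely any time after Visit 5 should return to the investigational site", there to have the assessments scheduled for the end-of-treatment (EOT) visit.

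The protocol's own list of populations (section 11.0.0) has ITT, per-protocol, safety and PK sets, and no mITT. The SAP introduces the mITT, and by its section 2 the SAP governs where the two documents differ.

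**The concern.** A treatment-policy estimand uses each child's outcome whether or not treatment was stopped. A set that admits only children who did not stop answers a different question: how did those who stayed on treatment fare? Claiming one estimand for all endpoints, while running every analysis on both sets, gives the mITT results a property they cannot have. The label adds to this, since modified ITT usually suggests a small departure from ITT rather than a completers analysis.

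The selection acts after baseline and may be related to outcome. Protocol section 9.4.5 lists clinically significant deterioration among the reasons for stopping. With 10 to 20 children, a few exclusions can move a mean noticeably, and the plan does not say which of two differing results would lead. At Week 6 the selection uses the future: a child with an observed Week 6 score who stops in, say, Week 9 is removed from the Week 6 mITT analysis.

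**Working it through.** **The plan's own figures.** SAP section 5.1 gives detectable CGI-I differences for a signed-rank test, two-sided 0.05, SD 0.7. They reproduce as a one-sample t-test at the reduced sample size floor(3N/π): 9 for N = 10 and 19 for N = 20. At power 0.80 / 0.85 / 0.90 this gives 0.747 / 0.800 / 0.866 and 0.476 / 0.509 / 0.551, against the stated 0.75 / 0.80 / 0.87 and 0.48 / 0.51 / 0.55. This point does not change them. They supply the SD and a yardstick.

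**Shift in the mean.** Let f be the fraction of children who stop early but have a score counted as EOT. Let gap be the completers' mean improvement minus the stoppers'. Then:

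ITT mean = (1 − f) × completers' mean + f × stoppers' mean

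mITT mean − ITT mean = f × gap

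The documents give neither f nor gap, so both are assumed: f from 10% to 30%, gap from 0 to 2 CGI-I points, with −1 added for stoppers who do better.

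| f | gap −1 | gap 0 | gap 0.5 | gap 1 | gap 2 |
|---|---|---|---|---|---|
| 10% | −0.10 | 0 | 0.05 | 0.10 | 0.20 |
| 20% | −0.20 | 0 | 0.10 | 0.20 | 0.40 |
| 30% | −0.30 | 0 | 0.15 | 0.30 | 0.60 |

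Positive values mean that the mITT looks better for the drug. The only programme figure is in Protocol section 5.6: two discontinuations with 16 children dosed across three studies, which is 2/16 = 12.5% and interim. At a one-point gap that gives 0.125 × 1 ≈ 0.13.

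**Dependence on observed scores.** Take 20 children, 4 stopping, completers' mean CGI-I 3.0 and stoppers' 4.0 (lower is better):

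- All four stoppers scored at EOT: ITT = (16 × 3.0 + 4 × 4.0)/20 = 3.2; mITT = 3.0.
- Two scored: ITT = (16 × 3.0 + 2 × 4.0)/18 = 3.11; mITT = 3.0.
- None scored: ITT and mITT are both 3.0, because section 9.2.1 excludes a child without an overall score at that visit.

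In the last case the two sets agree, but the ITT has then lost the stoppers as well. Whether they have a score depends partly on visit mapping. SAP section 5.2.5 does not say at which visit a last observation counts. Section 5.2.3 assigns unscheduled assessments to the most recently completed scheduled visit. No rule says that an early-termination assessment is EOT.

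**Effect on the test.** The exact signed-rank test was simulated with SD 0.7, 20% stopping, no true mean change among all enrolled, and 100,000 runs. The chance of a significant result in the drug's favour (nominal 0.025) in the completers set was:

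| N | gap −1 | gap 0 | gap 0.5 | gap 1 | gap 2 |
|---|---|---|---|---|---|
| 20 | 0.001 | 0.022 | 0.069 | 0.168 | 0.530 |
| 10 | 0.003 | 0.019 | 0.043 | 0.082 | 0.241 |

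With all enrolled children scored it stayed at or below 0.025.

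**The case against.** The strongest reply is that an analysis fitting the estimand is already pre-specified. The ITT runs in parallel for every endpoint, and the protocol asks for assessments after early cessation. A reader might infer that the efficacy analysis as a whole contradicts its estimand. The documents do not support that: the conflict is confined to the mITT results and to the missing statement of which set carries the estimand. This part of the reply stands.

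A reader might also infer that the mITT necessarily favours the drug. That is likely but not shown. Protocol section 9.4.5 also lists COVID-19, pregnancy, need for an excluded medication and a request to stop as reasons, none of which need relate to efficacy. Lack of benefit is not listed. Intolerance need not remove a child either, since Protocol sections 7.2.1 and 9.4.2 let a child continue on the highest tolerated dose and so complete. This stands too, and is why the range above includes zero and a reversal.

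Nor is the selection concealed. Section 3 of the SAP states the definition, section 6.1 reports the size of each population with discontinuations and reasons, and section 9.2 lists efficacy results by subject. The label is misleading, but the excluded children can be traced.

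Finally, there is no primary efficacy variable (SAP section 8.1), tests are descriptive (section 5), and efficacy is a secondary objective. This limits the consequence without removing it: Protocol section 6.2.2 looks for preliminary evidence of efficacy, and p-values will be reported to four decimals.

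**Conclusion.** The point holds for the mITT analyses. They condition on completing treatment, so they cannot estimate a treatment-policy effect, and the SAP neither gives them another estimand nor calls them supplementary. The ITT analysis can address the stated estimand to the extent that children who stop early have scores counted at EOT, and the SAP leaves that open.

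The size is unknown from the documents. Under the assumed range the mITT shows 0 to 0.6 CGI-I points more improvement than the ITT. The middle value of 0.2 is 0.2/0.55 ≈ 36% of the difference the plan says 20 children can detect at power 0.90. The difference is zero if nobody stops, if stoppers do as well as completers, or if no stopper has an EOT score; it reverses if stoppers do better. The consequence is moderate: it affects which secondary, descriptive result can be read as a treatment-policy result.

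**What to change.** Four changes to the SAP:

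1. Name the ITT as the main efficacy set for the treatment-policy estimand.
2. Rename the mITT set Completers, label it supplementary, and state that it does not estimate treatment policy.
3. State that early-termination assessments collected under Protocol section 9.4.5 are analysed as EOT in the ITT, and which assessment counts if a child also has one at Week 13. Without this, the ITT at EOT could shrink towards the completers and the first change would achieve little.
4. Report the number of children excluded from the completers set and their observed outcomes at Week 6 and EOT.

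The cost is SAP wording, table titles and one small extra table. No new data are needed. The headline result may be slightly less favourable.
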